5.4. Analysis Populations

Intent-to-Treat (ITT) – This population is defined as the population of participants (except non-Veterans and previous participants of this trial) who will be randomized to either of the transfusion strategy groups – Liberal or Restrictive. The participants will be categorized (in terms of their transfusion strategy assignment) based on their initial randomized group and will be included in analyses irrespective of their status – completer or drop out of the study before completion. The testing power for the primary endpoint is estimated as 90% in this population.

Modified Intent-to-Treat (mITT) – This population is defined as a subset of the ITT population that excludes randomized participants in a justified way, i.e., participants who are found to be ineligible (violating inclusion/exclusion criteria) or participating in more than one simultaneous intervention trial.

No-Recent-Transfusion – This population is defined as a subset of the ITT population excluding the participants who will receive transfusions within 30 days prior to or during the index operation, or after the index operation but before randomization.

Completers – This population includes all ITT participants who will complete all protocol-required lab and EKG assessments, hemoglobin monitoring and transfusion records in the hospital stay or until death, as well as completing assessments of the 5 individual components of the primary endpoint at 30 day and 90-day follow-up or until death.

Per Protocol – This population includes all ITT participants who will adhere to transfusion protocol in their assigned intervention groups.

Safety – This population includes all participants (except non-Veterans and previous participants of this trial) who will be randomized to either of the transfusion strategy groups – Liberal or Restrictive.

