Objective 1: To examine the effect of transfusion strategies on a composite endpoint of all-cause post-randomization mortality, myocardial infarction (MI), coronary revascularization, acute renal failure, or post-randomization stroke in Veterans at high cardiac risk undergoing open surgical interventions

Hypothesis 1: A significantly smaller proportion of participants receiving blood under a liberal transfusion strategy will experience the composite compared to participants under restrictive transfusion strategy at 90 days after randomization.

B. Secondary Objectives

Objective 1: To examine the effect of transfusion strategies on post-randomization infectious complications.

Hypothesis 1: A smaller proportion of participants receiving blood under a liberal transfusion strategy will experience post-randomization infectious complications compared to participants under restrictive transfusion strategy at 90 days after randomization.

Objective 2: To examine the effect of transfusion strategies on post-randomization cardiac complications other than MI.

Hypothesis 2: A smaller proportion of participants receiving blood under a liberal transfusion strategy will experience post-randomization cardiac complications other than MI compared to participants under restrictive transfusion strategy at 90 days after randomization.

Objective 3: To examine the effect of transfusion strategies on all-cause mortality during the one year post-randomization follow-up.

Hypothesis 3: A smaller proportion of participants receiving blood under a liberal transfusion strategy will die from any cause compared to participants under restrictive transfusion strategy during one year follow-up after randomization.

Objective 4: To examine the effect of transfusion strategies on a composite endpoint of all-cause post-randomization mortality, MI, coronary revascularization, acute renal failure, or post-randomization stroke at 30 days after randomization.

Hypothesis 4: A smaller proportion of participants receiving blood under a liberal transfusion strategy will experience the composite endpoint compared to participants under restrictive transfusion strategy at 30 days after randomization.

Objective 5: To examine the effect of transfusion strategies on the length of hospital stay

Hypothesis 5: Liberal transfusion strategy will lead to a shorter length of hospital stay.

C. Tertiary Objective

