- c. Veterans with past medical history of ischemic stroke/TIA of likely carotid origin, or history of IHD, or history of PAD (defined as prior intervention for PAD or ABIs < 0.9) who undergo the following Vascular Surgery operations: Open aneurysm repair (including but not limited to carotid, subclavian, abdominal aortic, iliac, femoral, or popliteal aneurysms); and complex endovascular aneurysm repair (defined as fenestrated endograft, or endograft with need for iliac conduit, or endovascular aneurysm repair with simultaneous femoral artery reconstruction or bypass). Subclavian/vertebral bypasses and transpositions are eligible with a history of PAD/IHD/ischemic stroke.

Patients undergoing the above procedures will be included in the study regardless of their preoperative Hb level, and regardless of preoperative or intraoperative transfusion they might have received. For non-compressible arteries and patients with diabetes, toe pressures (<60 mm Hg) may be used to identify prevalence of PAD.

B. Exclusion Criteria

- 1) Veteran unable to consent
- 2) Veteran unwilling to follow protocol (such as Jehovah's witnesses)
- 3) Veteran with known history of hereditary anemias such as Thalassemia or Sickle cell disease
- 4) Veteran with known history of hereditary bleeding disorders, such as factor VIII or factor IX deficiency
- 5) Veteran with prior history of adverse reaction to blood administration, such as fever, rash, or hemolysis
- 6) Veteran does not speak or understand English
- 7) Veteran hemodynamically unstable (systolic blood pressure <90 and heart rate >100 that persists for at least 30 minutes) or in cardiogenic shock for ≥ 48 hours after the index procedure

- 8) Veterans participating in another interventional trial
- 9) Pregnancy in female Veterans
- 10) Veteran is a prisoner or in custody of law enforcement
- 11) Prior randomization in the CSP#599
- 12) Patients who are known to have tested positive for COVID-19 and have not recovered prior to consent will not be consented. Any participant who is known to have a positive COVID-19 test during the screening process and has not recovered will be excluded prior to randomization.

Recovery from COVID-19 is defined as a patient who is asymptomatic (per local preoperative clearance policies) and at least 10 days post a positive test.

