Note: Patients may be screened, consented, and randomized once recovered, if not previously randomized. Veterans who test positive *after randomization but before discharge* must be terminated for study ineligibility. Veterans who test positive *after randomization and after discharge from the index admission*, may continue to participate in the study as long as follow up is completed remotely.

C. Recruitment

The site coordinator along with the local site investigator (LSI) will be primarily responsible for identifying each potential participant scheduled for an open surgical procedure. At the beginning of the study, vascular and general surgeons performing the operations of interest at a VAMC will be personally contacted by the Site coordinator to discuss logistical and procedural issues related to recruitment. Surgeons (both vascular and general surgeons) have been contacted in 15 primary and 8 back up VAMCs and have confirmed interest in participation in the study.

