Modified Intent-to-Treat (mITT) – This population is defined as a subset of the ITT population that excludes randomized participants in a justified way, i.e, participants who are found to be ineligible (violating major inclusion/exclusion criteria), such as non-Veterans, previous participants of this trial.

No-Recent-Transfusion – This population is defined as a subset of the ITT population excluding the participants who will receive transfusion(s) within 30 days prior to or during the index operation, or after the index operation but before randomization.

Completers – This population includes all ITT participants who will complete all assessments in the hospital stay, as well as 30 day and 90 day follow-up.

Per Protocol – This population includes all ITT participants who will adhere to transfusion protocol in their assigned intervention groups.

Safety – This population includes all participants who will be randomized to either of the transfusion strategy groups – Liberal or Restrictive.

The primary analysis of the study will be performed on the primary endpoint on the ITT population. The secondary analyses will be performed on the secondary and tertiary endpoints on the ITT population, as well as the analyses performed on all the primary, secondary, and tertiary endpoints on the mITT, No-Recent-Transfusion, Completers, and Per Protocol populations. SAE will be analyzed based on the Safety population.

2. Primary endpoint analysis

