- c. Veterans with past medical history of ischemic stroke/TIA of likely carotid origin, or history of IHD, or history of PAD (defined as prior intervention for PAD or ABIs < 0.9) who undergo the following Vascular Surgery operations: Open aneurysm repair (including but not limited to carotid, subclavian, abdominal aortic, iliac, femoral, or popliteal aneurysms); and complex endovascular aneurysm repair (defined as fenestrated endograft, or endograft with need for iliac conduit, or endovascular aneurysm repair with simultaneous femoral artery reconstruction or bypass). Subclavian/vertebral bypasses and transpositions are eligible with a history of PAD/IHD/ischemic stroke.

B. Exclusion Criteria

- 1) Veteran unable to consent
- 2) Veteran unwilling to follow protocol (such as Jehovah's witnesses)

- 3) Veteran with known history of hereditary anemias such as Thalassemia or Sickle cell disease
- 4) Veteran with known history of hereditary bleeding disorders, such as factor VIII or factor IX deficiency
- 5) Veteran with prior history of adverse reaction to blood administration, such as fever, rash, or hemolysis
- 6) Veteran does not speak or understand English
- 7) Veteran hemodynamically unstable (systolic blood pressure <90 and heart rate >100 that persists for at least 30 minutes) or in cardiogenic shock for \geq 48 hours after the index procedure
- 8) Veterans participating in another interventional trial
- 9) Pregnancy in female Veterans
- 10) Veteran is a prisoner or in custody of law enforcement
- 11) Prior randomization in the CSP#599
- 12) Patients who are known to have tested positive for COVID-19 and have not recovered prior to consent will not be consented. Any participant who is known to have a positive COVID-19 test during the screening process and has not recovered will be excluded prior to randomization.

Recovery from COVID-19 is defined as a patient who is asymptomatic (per local preoperative clearance policies) and at least 10 days post a positive test.

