Site surgeon concerned about resources needed for on-site follow-up (cost, time, etc.)																
No reliable method of follow-up contact with the participant (e.g., no phone, etc.)																
Primary reason participant preferred non-enrollment																
Primary reason surgeon preferred non-enrollment																
- Surgeon prefers restrictive transfusion for participant																
- Surgeon prefers liberal transfusion for participant																
- Surgeon believes participant has too short of life expectancy to be included																
- Surgeon believes participant is too high of a medical risk to be included																
- Reason other than transfusion preference																
Other Reason																

Table 5. Participant Disposition by Sites for All Randomized Participants (ITT)

Status	Buffalo	Cleveland	Dallas	Gainesville	Houston	Little Rock	Portland	Tampa	Loma Linda	Minneapolis	Asheville	Palo Alto	Pittsburgh	San Fran	Seattle	Long Beach	Total

Participant Study Status - Randomized Ppts																			
Completed																			
Discontinued																			
Reason for Termination																			
Participant completed study																			
Participant voluntarily withdrew																			
Participant lost to follow- up (location unknown)																			
Participant became pregnant																			
Participant was incarcerated																			
Administrative termination (e.g., non- compliance)																			
Participant relocated																			
Other																			
SAE other than death																			
Participant died																			

Table 6. Participant Disposition by Intervention Group for All Randomized Participants (ITT)

Status		Liberal	Restrictive	Total
Participant Study Status - Randomized Ppts	n			
Completed	n (%)			
Discontinued	n (%)			
Reason for Termination	n			
Participant completed study	n (%)			
Participant voluntarily withdrew	n (%)			
Participant lost to follow-up (location unknown)	n (%)			
Participant became pregnant	n (%)			
Participant was incarcerated	n (%)			
Administrative termination (e.g., non-compliance)	n (%)			
Participant relocated	n (%)			
Other	n (%)			
SAE other than death	n (%)			
Participant died	n (%)			

Table 6.1. List of Participants Who Are Administratively Terminated

Center number	Participant ID number	Group	Termination Date	Details

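### The SAP's mITT definition sets no pre-randomization limit on ineligibility, so it can drop participants for in-hospital COVID or co-enrolment that arose after randomization

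*SAP*

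**What the plan says.** - **SAP 5.4** defines the mITT set as the ITT set minus "participants who are found to be ineligible (violating inclusion/exclusion criteria) or participating in more than one simultaneous intervention trial". It gives no date for either ground and does not say that the decision is made without knowledge of arm or outcome.
- **Protocol XVI.E.1** is narrower. It excludes "participants who are found to be ineligible (violating major inclusion/exclusion criteria), such as non-Veterans, previous participants of this trial". Both examples are facts fixed before randomization. SAP 5.4 moves those two groups out of the ITT set instead, drops the restriction to major criteria, and adds co-enrolment as a separate ground.
- **Protocol VII.B, note after the exclusion criteria**, says that Veterans who turn COVID-positive after randomization and before discharge "must be terminated for study ineligibility". Those who turn positive after discharge from the index admission "may continue to participate in the study as long as follow up is completed remotely". SAP 4.2 repeats the exclusion criteria but omits this note.
- **SAP 4.2, exclusion 8**, already covers co-enrolment at entry: "Veterans participating in another interventional trial". SAP Table 7 codes simultaneous trial participation on a separate line from enrolment of an ineligible participant.
- **Protocol IV.B, Hypothesis 5**: "Liberal transfusion strategy will lead to a shorter length of hospital stay".
- **SAP 7** places the primary analysis on the ITT set. All primary, secondary and tertiary endpoints are also analysed on the mITT set as secondary analyses.

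**The concern.** Removing ineligible participants from an analysis set is safe when the ground was fixed before assignment and is applied without reference to arm, because randomization then balances it. That protection is lost when the ground can arise later. The Protocol itself attaches the word ineligibility to an in-hospital event after randomization, and SAP 5.4 excludes on ineligibility, so an analyst following both texts has reason to drop those participants.

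The COVID ground also depends on time in hospital: the same positive test counts before discharge and does not count after it. If stay is longer in one arm, as the trial hypothesises, that arm has more time at risk of exclusion, and longer stays plausibly go with complications. Treating physicians know the arm (SAP 4.1). At stake is whether an mITT result that departs from the ITT result reflects entry errors or selection after randomization.

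**Working it through.** **1. The plan's own figures.** The inputs from SAP 4.5 are 30% events in the restrictive arm, 22.5% in the liberal arm, two-sided 5% and 90% power. With pooled variance under the null and no continuity correction:

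n per arm = [1.960·√(2·0.2625·0.7375) + 1.2816·√(0.30·0.70 + 0.225·0.775)]² / 0.075² = 721.2, rounded up to 722, so 1444 in total. Then 1444/0.95 = 1520, or 760 per arm. Both stated figures reproduce and are not in dispute.

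**2. When each ground can arise.**

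| Ground | Text | Can it arise after randomization? |
|---|---|---|
| In-hospital COVID | Protocol VII.B note | Yes, explicitly, and it is labelled ineligibility |
| Simultaneous trial | SAP 5.4, second ground | Yes, because the wording is undated and goes beyond exclusion 8 |
| Non-Veteran, prior randomization | Protocol XVI.E.1 examples | No, fixed beforehand |

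**3. Size of the possible shift.** Let p be the common event rate under no treatment effect, e the share dropped in an arm, and q the event rate among those dropped, taken as the same in both arms. The event rate left in the arm is (p − e·q)/(1 − e), so

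false difference (liberal − restrictive) = (q − p)·[e_R/(1 − e_R) − e_L/(1 − e_L)].

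This is zero if e_R = e_L or if q = p. The documents give neither e nor q, so the values below are assumptions. Take p = (30% + 22.5%)/2 = 26.25% and q = 70%:

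- e = 2%: (0.2625 − 0.014)/0.98 = 25.36%
- e = 3%: (0.2625 − 0.021)/0.97 = 24.90%
- e = 4%: (0.2625 − 0.028)/0.96 = 24.43%

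Dropping 2% of liberal and 4% of restrictive gives 25.36 − 24.43 = 0.93 points, which is 0.93/7.5 = 12% of the design difference. Dropping 2% and 3% gives 0.46 points. For scale, the standard error of the difference at 760 per arm is √(2·0.2625·0.7375/760) = 2.26 points, so 0.93 points is about 0.4 standard errors.

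**4. Range over other assumed values.** With p = 30% in both arms, 760 per arm before exclusion, and a two-sided pooled z-test at 5%:

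| Dropped, liberal vs restrictive | q | False difference (points) | Type I error |
|---|---|---|---|
| 1% vs 1% | 30–90% | 0 | 5.0% |
| 1% vs 2% | 50–90% | 0.21–0.62 | 5.1–5.8% |
| 1% vs 3% | 50–90% | 0.42–1.25 | 5.4–8.3% |
| 2% vs 5% | 50–90% | 0.64–1.93 | 5.8–13.1% |
| Any of these | 30% | 0 | 5.0% |

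Lost numbers are not the issue. If exclusion is neutral between arms and the 30% and 22.5% rates hold, power is 91.4% with none dropped, 90.9% at 2% dropped and 90.0% at 5%.

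**The case against.** The best defence is that a participant found to be ineligible ordinarily means one whose entry violation is discovered later. The SAP's tables lean that way. Table 3 lists shock, co-enrolment, custody and pregnancy as reasons for ineligibility for randomization, and its COVID row concerns positivity after consent but before randomization. Because SAP 4.2 omits the Protocol's note, the SAP does not prescribe dropping the in-hospital COVID cases. This stands in part: the text is ambiguous and does not command the exclusion. But one analyst could apply the Protocol note and another the SAP list, and each would have textual support for a different mITT set.

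A reader might infer more: that every exclusion criterion arising after randomization removes a participant. The documents do not support that.

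- **Shock.** The criterion reads "or in cardiogenic shock for ≥ 48 hours after the index procedure", and Protocol X requires randomization within 24 hours of the first low haemoglobin, so the 48 hours can end after randomization. Nothing says how often this happens, and nothing makes shock after randomization an ineligibility.
- **Custody and pregnancy.** SAP Tables 5 and 6 list "Participant was incarcerated" and pregnancy as termination reasons. Termination is not exclusion from the mITT set, and no text equates the two.

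It is also fair to say that the size is hypothetical. No document gives an exclusion share, and nothing supports a 70% event rate among participants with in-hospital COVID or co-enrolment. The shorter stay is a hypothesis, and no text links co-enrolment to arm. In the assumed cases the shift works against the liberal arm; with a lower event rate among those dropped, or more dropped from the liberal arm, it would reverse.

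**Conclusion.** The point holds for two grounds: in-hospital COVID, which the Protocol explicitly labels ineligibility after randomization, and co-enrolment, which SAP 5.4 leaves undated. On these the mITT set can condition on post-randomization events, and the COVID window depends on a quantity the trial expects to differ by arm.

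Bias is possible, not demonstrated. Under the assumed shares (1–5%) and event rates among those dropped (30–90%), the false difference runs from 0 to 1.9 points and the type I error of the mITT comparison from 5.0% to 13.1%. The upper ends need both a marked imbalance and a very high event rate among those dropped. These figures also assume that the 90-day outcomes of those dropped are known.

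A reader might infer that the trial's main conclusion is at risk. It is not: the primary test is on the ITT set, which keeps participants whether or not they complete. The point is worth correcting because the mITT set is pre-specified for every efficacy endpoint and will be read beside the ITT result.

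**What to change.** Add to SAP 5.4, in substance: *The mITT set excludes only participants who failed an inclusion or exclusion criterion on facts existing before randomization. COVID positivity or participation in another trial that began after randomization is not a ground for exclusion. The flag is derived without reference to arm or outcome.* Report mITT exclusions by arm and reason.

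Reconcile this text with the mITT definition in Protocol XVI.E.1, and reconcile the Protocol VII.B note with SAP 4.2. This concerns the analysis set only. It takes no position on when participation should be terminated.

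The cost is one SAP passage and one derived flag, with no effect on the ITT analysis. There is one small downside. Participants terminated under the Protocol note may have incomplete 90-day data, since active event monitoring stops at termination (Protocol XI.D). Keeping them in the mITT set means handling them under SAP 5.2, through VA database capture and, where used, multiple imputation. The ITT analysis already has to do this for the same people. The change should be made before the SAP is finalized and the database locked (SAP 5.1).

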Recruitment rates at the eight active sites will be closely monitored during this phase. The initial eight sites are each expected to enroll 36 participants in the first year of the study, for a total of 288 participants at the end of the first year. The actual recruitment experience of the eight sites in the first year will be used to revise the projected recruitment rate for the remainder of the study and may lead to a lengthening or shortening of the total recruitment period, as appropriate. Measures to address unexpectedly low recruitment rates during this feasibility phase have been described on page 14. At the completion of the feasibility phase, the study will be moved to a continuation phase where the remaining 7 sites will be activated and the remaining participants (1232 participants) will be recruited and followed up.

E. Data Analysis Plan

The primary analysis will be performed to test the null hypothesis of no difference in composite outcome of all-cause mortality, MI, coronary revascularization, acute renal failure, or post-randomization stroke between participants randomly assigned to a 10 gm/dl Hb transfusion strategy compared to participants assigned to 7 gm/dl transfusion strategy. If the null hypothesis is not rejected, a 95% confidence interval will be constructed about the difference observed to inform the medical community as to how large the difference is likely to be in either direction. All statistical tests will be two-sided and the primary outcome will be tested at 5% level of significance. SAS 9.4 or higher will be used to conduct all the statistical analyses. A variety of analytic methods will be used for the primary endpoint, secondary endpoints, tertiary endpoints and other analyses (TABLE 4).

1. Analysis Populations

Intent-to-Treat (ITT) – This population is defined as the population of participants who will be randomized to either of the transfusion strategy groups – Liberal or Restrictive. The participants will be categorized (in terms of their transfusion strategy assignment) based on their initial randomized group and will be included in analyses irrespective of their status – completer or drop out of the study before completion. The testing power for the primary endpoint is estimated as 90% in this population.

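### SAP 5.4 takes non-Veterans and previous participants out of the Safety and ITT sets, against the protocol, so their SAEs and deaths would be missing from SAP Tables 29 to 31

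*SAP*

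**What the plan says.** Protocol XVI.E.1 defines three of the sets as follows.

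- **ITT:** "This population is defined as the population of participants who will be randomized to either of the transfusion strategy groups". There is no exception.
- **Safety:** "This population includes all participants who will be randomized to either of the transfusion strategy groups – Liberal or Restrictive". Again there is no exception, and the same section bases the SAE analysis on this set.
- **mITT:** a subset of ITT without "participants who are found to be ineligible (violating major inclusion/exclusion criteria), such as non-Veterans, previous participants of this trial". This is the only definition in which the two groups are named.

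SAP 5.4 changes the first two.

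- **ITT** becomes "the population of participants (except non-Veterans and previous participants of this trial) who will be randomized".
- **Safety** becomes: "Safety – This population includes all participants (except non-Veterans and previous participants of this trial".
- **mITT** still removes participants who break other eligibility criteria or who are in a second interventional trial at the same time.

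The primary analysis is run on ITT (Protocol XVI.E.1, SAP 7), and all safety analyses are run on Safety (SAP 8). SAP 8.1 promises an SAE incidence table (Table 29) and a list of SAEs in which a randomized participant died (Table 30). Table 31 gives the laboratory data. All three are labelled as Safety-set tables. Protocol XVI.H says that departures from the protocol's statistical plan will be specified in the SAP.

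**The concern.** Two governing documents define the primary and the safety population differently, and the SAP gives no reason for its version.

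Safety is the more serious half. A safety set should hold everyone who was put on an assigned strategy, whether or not they should have been enrolled. Under SAP 5.4 a person randomized in error because they are not a Veteran, or because they had been randomized before, drops out of the tables altogether. A person randomized in error despite a hereditary anemia or a prior transfusion reaction stays in. Nothing about safety explains that difference.

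At stake is whether the final safety tables are complete. One death in a removed participant would make Table 30, which is described as covering randomized participants, incorrect. For ITT the stake is mainly labelling: SAP Tables 5 and 6 are titled as covering all randomized participants (ITT), and under SAP 5.4 that would not be exact.

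**Working it through.** The point rests on comparing definitions. Arithmetic only bounds its effect.

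**1. Who is in which set**

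| Randomized participant | Protocol ITT and Safety | SAP ITT and Safety | mITT, either document |
|---|---|---|---|
| Eligible | in | in | in |
| Non-Veteran | in | out | out |
| Previous participant | in | out | out |
| Breaks another major criterion | in | in | out |

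The documents differ in ITT and Safety only for the two named groups.

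**2. What happens to their SAEs**

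- Collection: Protocol XI.D starts active SAE monitoring at randomization, runs it to day 90 or termination, and records and expedites all SAEs whether related or not. It makes no exception for ineligible participants.
- Review: the study pharmacist reviews all SAEs, and the DMC receives summaries (Protocol XI.D, XVII.C and XVII.E).
- Reporting: SAP 8 sends all safety output through the Safety set, so these events do not reach Tables 29 to 31. No other SAP table or listing reports them. Table 7 counts ineligible enrolments as deviations but carries no events.

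**3. The plan's sample size, reproduced**

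Inputs (Protocol XVI.B, SAP 4.5): 30% and 22.5% event rates, two-sided 5%, 90% power, 5% dropout. The mean rate is 0.2625.

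n per arm = [z(0.975)·√(2 × 0.2625 × 0.7375) + z(0.90)·√(0.30 × 0.70 + 0.225 × 0.775)]² / 0.075²

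= [1.960 × 0.6222 + 1.2816 × 0.6200]² / 0.005625 = 4.057 / 0.005625 ≈ 721.2, rounded up to 722.

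The total is 1,444, and 1,444 / 0.95 = 1,520. Both match the plan.

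**4. Effect of the carve-out on power**

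The documents do not say how many people would be removed, so k below is an assumption. With n = (1,520 − k) × 0.95 / 2 per arm,

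power = Φ{[0.075·√n − 1.960 × 0.6222] / 0.6200}.

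| k removed | Share of 1,520 | Power after 5% dropout |
|---|---|---|
| 0 | 0% | 90.0% |
| 5 | 0.33% | 89.9% |
| 10 | 0.66% | 89.8% |
| 15 | 0.99% | 89.7% |
| 30 | 1.97% | 89.5% |

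Even at 30 the loss is about 0.6 percentage points.

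**5. Effect on the death listing**

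As an illustration only, take the protocol's own 90-day death rates from its Table 2 (6.9% and 15.3% in the two nadir-hemoglobin bands). With k = 10, the expected number of deaths missing from Table 30 is 10 × 0.069 = 0.7 to 10 × 0.153 = 1.5. Those rates come from VA patients followed from operation, so they are only a rough guide.

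**The case against.** The case for leaving the SAP alone has real content.

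- **The ITT exclusion can be defended.** Veteran status, and prior randomization at the time of a second entry, are both fixed before the assignment concerned, so removal is not driven by arm or outcome. The study question is about Veterans, and prior randomization is an exclusion criterion (Protocol VII.B, item 11). Restoring ITT without a further rule could enter one person twice in a Pearson test that assumes independent observations. This stands. It is why the ITT remedy needs either a rule or a declaration, not simple reinstatement.
- **The wording on previous participants is ambiguous.** SAP 5.4 classifies people by their initial randomized group, so it may mean that only the second entry is dropped. If the whole person were dropped, removal of the first entry would depend on something that happened after it. The text does not settle which is meant.
- **The change is visible.** The new definitions are written out in SAP 5.4, and the SAP's front pages were not available, so a change note there cannot be ruled out. What is missing from the available text is a label and a reason.

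A reader might also infer more than the documents support:

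- That SAEs of ineligible participants in general are lost. Only the two named groups are affected.
- That those removed were all transfused. A restrictive-arm participant whose hemoglobin never falls below the trigger may receive no blood. The omission applies either way.
- That safety oversight is weakened. Collection, expedited reporting, pharmacist review and DMC summaries are not tied to the Safety set.
- That the mITT will lose people who qualified by toe pressure, because SAP 4.2 omits the protocol's note ("For non-compressible arteries and patients with diabetes, toe pressures (<60 mm Hg) may be used to identify prevalence of PAD"). Nothing says that mITT eligibility will be re-judged from SAP 4.2 alone. The note also matters only where PAD history is the sole route to eligibility.

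None of this gives a reason to leave collected SAEs of randomized people out of the safety tables.

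**Conclusion.** The contradiction is real for both sets. For Safety, the SAP rule should not stand as written: followed literally, it omits from Tables 29 to 31 every SAE and death in two groups of randomized participants, while two of those tables are titled as covering the randomized. For ITT it is an undeclared departure from the protocol that may be defensible once declared.

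The size is small. The documents give no count, both conditions are screened for at entry, and zero is possible. On an assumed 0 to 10 people of 1,520, at most 0.66% of the primary set is affected and power stays between 89.8% and 90.0%. It would be wrong to infer that the primary result is biased or materially weakened. The case for acting rests on complete safety reporting and on agreement between the two documents, not on power.

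**What to change.** 1. **Safety (SAP 5.4):** restore the protocol definition, all randomized participants. Report a repeat participant's events once, under the assignment in force when they occurred, and footnote anyone who appears in both arms' denominators.
2. **ITT (SAP 5.4):** choose one of two routes.
   - Restore the protocol definition, with a rule that a repeat participant is analysed once, under the first randomization; the two groups then leave at mITT only.
   - Keep the exclusion, declare it as a deviation under Protocol XVI.H with reasons, say whether it removes the person or only the second entry, and list the removed participants by assigned arm with their primary outcome. In that case, retitle Tables 5 and 6.
3. **Editorial note, optional:** add the protocol's toe-pressure note to SAP 4.2 so that the two eligibility texts agree.

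The cost is SAP wording and, on the second ITT route, one short listing. No new data are needed, because SAEs are already collected from randomization. The change should be made before the SAP is finalized and the database locked.
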